5.9 Exposure in Part C

Extent of study drug exposure will be summarized for flare-up based treatment and non-flare-up based treatment.

5.9.1 Exposure to Flare-up Based Treatment

The summary of exposure by subject across all flare-up cycles will be included:

- Duration of flare-up treatment by subject across all flare-up cycles, defined as sum of days of exposure across all flare-up cycles (see [Section 3.2.3](#) for calculation)
- Duration of flare-up treatment by subject according to the following categories:
 - ≤ 3 months
 - $>3 - \leq 6$ months
 - $>6 - \leq 9$ months
 - $>9 - \leq 12$ months
 - $>12 - \leq 15$ months
 - $>15 - \leq 18$ months
 - $>18 - \leq 21$ months
 - $>21 - \leq 24$ months
 - >24 months
- Duration of high flare-up treatment by subject (20-mg dose)
- Duration of low flare-up treatment by subject (10-mg dose)

The summary of exposure by flare-up cycle will be included:

- Duration of flare-up treatment by flare-up cycle
- Duration of flare-up treatment by flare-up cycle, according to the following categories:
 - ≤ 2 weeks
 - $>2 - 4$ weeks
 - $>4 - 6$ weeks
 - $>6 - 8$ weeks
 - $>8 - 10$ weeks

- >10 – 12 weeks
- >12 – 16 weeks
- >16 – 20 weeks
- >20 weeks
- Duration of high flare-up treatment by flare-up cycle (20-mg dose)
- Duration of low flare-up treatment by flare-up cycle (10-mg dose)

If a subject has dose reduction, the exposure is counted by planned treatment.

The following summaries will also be presented for Flare-up Treated Population:

- Number of days after flare-up onset to first dose of study drug for flare-up cycles, calculated as sum of (date of first dose of flare-up cycle – date of flare-up onset + 1) across all flare-up cycles

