5.6 Treated Flare-ups Starting During Part B

The number of treated flare-ups will be summarized with counts and percentages of subjects in the Flare-up Population and Flare-up PP Population. Similar summaries will be provided for the number of flare-ups with dosing extended beyond 12 weeks, the number of flare-ups for which an interruption of study drug occurred during flare-up dosing, and the number of flare-ups for which study drug was discontinued during flare-up dosing.

Treated flare-up data as reported by the subject and the Investigator including symptoms, probable causes, and location(s) will be summarized for the Flare-up and Flare-up PP Populations.

The number of days after flare-up onset to the date of first dose of study drug for the flare-up will be summarized for the Flare-up Population with descriptive statistics.

Data for untreated flare-ups will be listed.

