If the subject experiences intolerable side effects, the dose may be reduced to the next lower dose; if the subject is already receiving the lowest possible dose as shown in the Table 1, then study drug will be discontinued. Treatment may be extended after the 84-day treatment period (flare-up based dosing) if the flare-up is ongoing and continue until the flare-up resolves. Dosing will be extended in 4-week intervals based on clinical signs and symptoms as assessed by the Investigator, with remote visits performed every 4 weeks while on treatment. In the event the subject requires dose de-escalation due to an intolerable side effect for a previous flare-up, then the dose the subject will receive for a subsequent flare-up will be determined by the Investigator and the Medical Monitor.

Should a subject experience an intercurrent flare-up (defined as a new flare-up or marked worsening of the original flare-up), or if the Investigator confirms the presence of a substantial high-risk traumatic event likely to lead to a flare-up, at any time during flare-up based treatment, the 12-week dosing regimen will restart upon new intercurrent flare-up confirmation by the Investigator (ie, 4 weeks of 20 mg palovarotene followed by 8 weeks of 10 mg palovarotene [or weight-based equivalent]). A Flare-up Cycle will include the first flare-up or traumatic event and any subsequent intercurrent flare-ups or traumatic event during the same dosing period. Flare-Up Cycle Safety Day 1 is defined as the first day that study drug is administered for the first flare-up or traumatic event during that cycle. Safety assessments will be performed on Flare-up Cycle Safety Day 1, at 4 weeks, and every 8 weeks thereafter until treatment of the last flare-up or traumatic event in the Flare-up Cycle is completed. If any flare-up in a cycle has not resolved after 12 weeks, treatment and safety assessments will be extended and 10 mg palovarotene (or the weight-based equivalent) will be administered in 4-week intervals until all the flare-ups resolve and flare-up based treatment has been completed. It is possible that subjects may experience more than one Flare-up Cycle during the study.

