3.2 Part C Study Day, Flare-up Cycle Days and Non-Flare-up Days

3.2.1 Part C Study Day 1

For all subjects, Part C Study Day 1 is defined as the date of informed consent in Part C. Part C Study Day -1 will be the day immediately prior to Part C Study Day 1.

3.2.2 Flare-up Cycle and Flare-Up Cycle Day 1

- A Flare-up Cycle will include the first flare-up and any subsequent intercurrent flare-ups during the same dosing period.
- Flare-Up Cycle Day 1 is defined as the first day that study drug is administered for the first flare-up during that cycle.

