5.7 Treated Flare-ups Starting During Part C

Treated flare-ups for flare-up based treatment during Part C will be summarized for Flare-up Treated Population and Flare-up Per Protocol Population including following variables:

- Total number of flare-up cycles
- Number of flare-up cycles with dosing extended beyond 12 weeks
- Number of flare-up cycles for which an interruption of study drug occurred during flare-up dosing overall and by high or low flare-up based doing. Where an interruption includes ≥ 14 days without dosing.
- Number of flare-up cycles with dosing reductions overall and by high or low flare-up based doing
- Number of flare-up cycles for which study drug was discontinued during flare-up dosing overall and by high or low flare-up based doing
- Total number of treated flare-ups across all flare-up cycles
- Number of flare-ups treated per cycle
- Number of flare-ups treated per cycle categorized
 - 1 flare-up
 - 2 flare-ups
 - 3 flare-ups
 - 4 flare-ups
 - >5 flare-ups
- Number of intercurrent flare-ups treated per cycle
- Number of palovarotene treated trauma flare-ups

A dose interruption is defined as dosing interrupted for at least 14 days without dosing.

Number of subjects with treated flare-ups will also be summarized for Flare-up Treated Population including following variables:

- Number of subjects with treated flare-up cycles
- Number of subjects with treated flare-up cycles by categories
 - 1 flare-up cycle
 - 2 flare-up cycles
 - 3 flare-up cycles
 - 4 flare-up cycles
 - ≥ 5 flare-up cycles
- Number of subjects with flare-up cycle with dosing extended beyond 12 weeks
- Number of subjects for which an interruption of study drug occurred during flare-up cycle dosing overall and by high or low flare-up based doing
- Number of subjects for which study drug was discontinued during flare-up cycle dosing overall and by high or low flare-up based doing

- Number of subjects with dose reduction during flare-up cycle dosing overall and by high or low flare-up based dosing

Treated flare-up data as reported by the subject and by Investigator including symptoms, probable causes, and location(s) will be summarized for the Flare-up Treated Population.

Flare-up location mapping is described in [Table 11](#).

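### Part C defines the delay from flare-up onset to first dose as a sum across all flare-up cycles, so the reported figure is not a delay and cannot be set beside Parts A and B

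*SAP*

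**What the plan says.** The Part C SAP, section 5.9.1, lists one further summary for the Flare-up Treated Population after the exposure durations: "Number of days after flare-up onset to first dose of study drug for flare-up cycles, calculated as sum of" a bracketed difference, which reads "date of first dose of flare-up cycle – date of flare-up onset + 1) across all flare-up cycles". The section does not divide by the number of cycles, gives no per-cycle version and does not say whether the sum is taken within a subject.

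Part C expects some subjects to contribute several terms. Section 2.3 says "It is possible that subjects may experience more than one Flare-up Cycle during the study". Section 5.7 plans a table headed "Number of subjects with treated flare-up cycles by categories", running from one cycle to five or more. A cycle is not the same as a flare-up. By section 3.2.2, "A Flare-up Cycle will include the first flare-up and any subsequent intercurrent flare-ups during the same dosing period".

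The Part B SAP, section 5.6, handles the same quantity per flare-up: "The number of days after flare-up onset to the date of first dose of study drug for the flare-up will be summarized" with descriptive statistics. The Part A SAP, section 6.8, has the same rule for its Treated Population. Neither sums.

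**The concern.** Time from onset to first dose belongs to a single treated episode. Exposure is different: it accumulates, so the first bullet of section 5.9.1 rightly sums days of treatment over cycles. Applied to a delay, the same operation mixes how late treatment started with how often it was started.

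Prompt treatment is part of the regimen. Section 2.4 of Part B wants treatment begun without delay once a flare-up is reported and confirmed, and section 2.3 of Part C ties the first dose to the Investigator's confirmation. This bullet is the only place where the Part C SAP describes the interval from onset to dose. Followed as written, it would misstate that interval for every subject with more than one cycle. It would also give a figure on a different footing from Parts A and B.

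**Working it through.** The SAP states no numerical value for this variable, so there is no figure of its own to reproduce. The check evaluates the stated formula.

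**Inputs**
- Summand, from Part C 5.9.1: first-dose date of the cycle − onset date + 1.
- Range of the sum, from the same place: all flare-up cycles.
- Number of cycles per subject, k: the documents give no distribution. Values of 1 to 5 are assumed, in line with the categories in section 5.7.
- True delay in each cycle, d: not given. Values of 0 to 7 days are assumed.
- Unit of the sum: not stated. Per subject is assumed.

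**Formula.** With the same delay d in each of k cycles, where d = first-dose date − onset date:

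value = Σ(d + 1) = k(d + 1) = kd + k

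The term kd comes from the summing. The added k comes from the extra day in each cycle.

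**Results, k(d + 1), in days**

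| True delay d | k = 1 | k = 2 | k = 3 | k = 4 | k = 5 |
|---|---|---|---|---|---|
| 0 | 1 | 2 | 3 | 4 | 5 |
| 2 | 3 | 6 | 9 | 12 | 15 |
| 3 | 4 | 8 | 12 | 16 | 20 |
| 5 | 6 | 12 | 18 | 24 | 30 |
| 7 | 8 | 16 | 24 | 32 | 40 |

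Each row has one true delay, yet the value rises in proportion to the number of cycles.

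**The two effects apart, at d = 3.** With one cycle, 3 + 1 = 4: the sum does nothing and the whole excess is the extra day. With four cycles, 4 × 3 = 12 comes from summing and 4 × 1 = 4 from the extra days, giving 16.

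**Ordering.** One cycle treated after 7 days gives 1 × (7 + 1) = 8. Four cycles each treated after 2 days give 4 × (2 + 1) = 12. The subject treated sooner each time has the larger value. Without the extra day the order is still wrong, 7 against 8, so the sum alone is enough to reverse it.

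**Pooled reading.** If the sum runs over all cycles in the population, the result is a single total of days. It has no distribution to summarize and is not a delay.

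**After the correction.** With one record per cycle and no sum, the value is d whatever k is: 0, 3 and 7 days stay 0, 3 and 7.

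**The case against.** The strongest reply is that a per-cycle summary was intended. The bullet stands outside the by-subject list, its label refers to flare-up cycles, and section 2.4 of Part C bases flare-up analyses on cycles. The closing words could have been carried over loosely from the exposure bullet above. That is possible, but the instruction is to sum, and a programmer who reported each cycle separately would be departing from the written plan. What stands is that the per-subject unit is an inference.

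Four stronger readings are tempting, and the documents do not support them:

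- A reader might infer that subjects with more flare-ups appear to be treated later. The sum runs over cycles. Several intercurrent flare-ups within one cycle add only one term, and section 5.7 counts cycles and flare-ups separately.
- A reader might call the extra day an error in itself. Part C counts days inclusively in sections 3.2.3, 3.2.4, 5.8, 5.9.4 and 5.10. Here it sits badly with a label that speaks of days after onset, because same-day dosing scores 1. That is a minor point of labelling. Parts A and B give no formula, so they differ from Part C visibly in the unit, but it cannot be shown that they differ in the extra day.
- A reader might take the table above as the size of the distortion in this trial. The documents give neither the delays nor the distribution of cycles per subject, so the realized size is unknown.
- A reader might carry the problem over to the efficacy results. The variable enters no primary or secondary endpoint (6.1, 6.2), compliance calculation (5.10) or population definition (section 4). The covariate for time since last flare-up in section 3.4 is a different quantity.

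**Conclusion.** The rule is wrong as written. On neither reading of the unit does it return a delay: per subject it gives k(d + 1), and pooled it gives one total. The first result rests on the per-subject assumption; the delays and cycle counts in the illustration are assumed too. The conflict with the per-flare-up summaries of Parts A and B is in the text and needs no assumption. The consequence is limited to one descriptive line of the exposure section, which should be corrected but alters no efficacy or safety conclusion.

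**What to change.** In Part C 5.9.1, delete the sum. Define the delay for each flare-up cycle as the date of first dose of the cycle minus the onset date of the first flare-up in that cycle. Naming the first flare-up also settles which onset date applies when a cycle contains several, which the present text leaves open. If the extra day is kept for consistency with the rest of Part C, label the figure as an inclusive count.

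Summarize with the cycle as the unit. If a subject-level figure is wanted, use the mean of the subject's per-cycle delays.

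The text change is one line. Any output already produced under the present wording should also be checked. Section 1.1 says that the final report is not meant to rerun tables from the interim reports, and section 11 does not list 5.9.1 among the key changes. The documents do not say whether this summary has already been produced.

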5.9.2 Exposure to Non Flare-up Based Treatment

The following summary will be included:

- Number of subjects with non-flare-up based treatment
- Duration of non-flare-up based treatment (months), defined as days subjects received non-flare-up treatment/30.5 (see Section 3.2.4 for calculation)
- Number of subjects by following exposure categories in months:
 - >0 – 6 months
 - >6 – 12 months
 - >12 – 18 months
 - >18 – 24 months
 - >24 months
- Number of subjects with at least one non-flare-up dose reduction
- Number of dose reductions by type (e.g. 5 to 2.5 mg)
- Number of subjects with study drug interruption, where a dose interruption is defined as dosing interrupted for at least 14 days without dosing
- Number of subjects with study drug discontinuation

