1.1 Context for Version 1.1

This statistical analysis plan amendment is introduced in preparation for the writing of the final CSR, which will include summaries of data collected after the start of the prolonged palovarotene dosing interruption that started in late 2019/early 2020 described below and up to LPLV in late 2022. This includes data from subjects who restarted palovarotene after the interruption and subjects who did not restart. The final CSR is not intended to include a rerun of tables and content already included in the interim CSRs from 2021 and 2022.

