Based on additional post-hoc analyses presented to the DMC on January 21, 2020, the DMC noted that using the square-root transformation of the data in the primary analysis appears to have moved the statistical conclusion from significant therapeutic benefit to showing futility of the treatment. The DMC also noted that the dilemma created by these highly disparate results precludes a confident conclusion about futility. As such, the DMC recommended that additional analyses be conducted and provided to them for consideration at the next interim analysis.

US FDA instituted a partial clinical hold on dosing of palovarotene due to premature physéal closure (PPC) for subjects <14 years of age on December 4, 2019; as of the finalization of this SAP amendment, dosing

has not yet resumed for these subjects. Dosing on all other subjects in Study 301 and Study 202 Part C not subject to US FDA's partial clinical hold was interrupted following the January 21, 2020 DMC meeting while the protocol amendment allowing the continuation of the study after the futility outcome and incorporating the additional analyses requested by the DMC was reviewed by regulatory agencies, IRBs, and investigational sites. These subjects had palovarotene dosing interrupted on or around January 24, 2020. The sponsor allowed dosing to resume as of March 26, 2020, provided each individual site had obtained Ethics Committee approval to do so and the site was able to fulfil regulatory and operational requirements. Subjects were expected to restart dosing over a span of weeks due to these logistical considerations.

2 Overview

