2.3 Study Treatment

As of 04 December 2019, all subjects <14 years of age were required to interrupt study drug due to a partial clinical hold placed on the palovarotene clinical development program by the US FDA. Treatment will subsequently not be restarted in children < 14 years of age.

Subjects and/or their parents/caregivers will report potential flare-up symptoms to site personnel; such symptoms include, but are not limited to, pain, swelling, redness, decreased range of motion, stiffness, and warmth. Only one symptom is required to define a flare-up. If these symptoms are consistent with previous flare-ups, include a subject reported onset date, and are confirmed by the Investigator as associated with a flare-up, subjects will receive open-label palovarotene treatment as follows:

- 20 mg for 4 weeks (28 days) once daily. The first dose will be taken upon flare-up confirmation by the Investigator. To be followed by:
- 10 mg for 8 weeks (56 days) once daily, for a total flare-up treatment duration of 12 weeks (84 days); 10 mg treatment may be extended if the flare-up is ongoing and continue until the flare-up resolves. Dosing will be extended in 4-week intervals and be based on clinical signs and symptoms as assessed by the Investigator.

Flare-up based dosing should also be initiated if the Investigator confirms the presence of a substantial high-risk traumatic event likely to lead to a flare-up.

All dosing, regardless of non-flare-up or flare-up based, will be weight-adjusted in subjects under the age of 18 years with less than 90% skeletal maturity on hand/wrist radiography at Screening. (Note: all weight-based dosing will cease when subjects achieve $\geq 90\%$ skeletal maturity based on hand/wrist radiography, but radiographic assessment of the growth plate will continue until these subjects achieve 100% skeletal maturity at both knee and hand/wrist locations.)

Table 1: Weight-Adjusted Palovarotene Doses and Dose De-Escalation Doses

Weight Range Category	20-mg Equivalent	15-mg Equivalent	10-mg Equivalent	7.5-mg Equivalent*	5-mg Equivalent*	2.5-mg Equivalent*
20 to <40 kg	12.5 mg	10 mg	6 mg	4 mg	3 mg	1.5 mg
40 to <60 kg	15 mg	12.5 mg	7.5 mg	5 mg	4 mg	2 mg
≥ 60 kg	20 mg	15 mg	10 mg	7.5 mg	5 mg	2.5 mg

* In the event of dose de-escalation from 20-mg, 10-mg, or 5-mg equivalent, respectively.

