3.2.4 Duration of Non-Flare-up Treatment

Based on study design, subjects are assumed to be on non-flare-up based treatment from the date they received first non-flare-up treatment unless they receive flare-up based treatment. Thus, duration of non-flare-up treatment (days) will be calculated as (last non-flare-up treatment date - first non-flare-up treatment

date – duration of flare-up treatment (days) - days where non-flare-up meds were not taken/interrupted + 1). Duration of flare-up treatment (days) is defined in 3.2.3.

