5.10 Compliance

Compliance is defined as (duration of treatment/expected duration of treatment). Calculation of duration of treatment is described in Section 3.2.3 and 3.2.4.

The expected duration of treatment is calculated as following:

- For non-flare-up treatment, expected duration of treatment is calculated as (last non-flare-up dose date – first non-flare-up dose date) – (sum of (all Flare-up cycle dosing periods)) + 1.
- For flare-up treatment, expected duration of treatment is calculated as total of expected flare-up cycle dosing periods across all flare-up cycles. Each expected flare-up cycle dosing period is defined as (last flare-up cycle dose date – first flare-up cycle dose date + 1).

Compliance will be summarized for the Treated Population with descriptive statistics. Compliance in category (<80%, ≥80%) will also be summarized for counts and percentages of subjects.

6 Efficacy Data

Unless otherwise stated, efficacy data will be summarized using Enrolled Population presented by groups: PVO 20/10 mg Only, PVO 5 mg, PVO Total and Never Received PVO Treatment. The PVO 20/10 mg Only group only includes subjects who did not take PVO 5 mg.

Imaging Reads

Imaging data includes results from low-dose WBCT scans (excluding head) and radiographs.

WBCT HO status and total HO volume or new HO volume will be summarized by visit. Those analysis will be included in the interim CSR. All other analysis will be presented in the final CSR.

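### Part C compliance charges the imposed dosing pause to subjects who restarted, and the interruption count cannot separate that pause from subject-level interruptions

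*SAP*

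**What the plan says.** All references are to the Part C SAP.

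- **Interruption.** Section 5.9.2 lists the "Number of subjects with study drug interruption, where a dose interruption is defined as dosing interrupted for at least 14 days without dosing". Section 5.7 applies the same rule to flare-up cycles: "A dose interruption is defined as dosing interrupted for at least 14 days without dosing". Neither distinguishes causes.
- **Compliance.** Section 5.10 defines it as duration of treatment over expected duration. The numerator comes from sections 3.2.3 and 3.2.4; section 3.2.4 subtracts "days where non-flare-up meds were not taken/interrupted", and section 3.2.3 does the same within flare-up cycles. The denominator is introduced by "For non-flare-up treatment, expected duration of treatment is calculated as" and is the last minus the first non-flare-up dose date, less flare-up cycle dosing periods, plus 1. For a flare-up cycle it is last minus first cycle dose date, plus 1. Neither denominator subtracts a pause.
- **The pause.** Section 1.1 speaks of the "prolonged palovarotene dosing interruption that started in late 2019/early 2020". Section 2.3 states: "As of 04 December 2019, all subjects <14 years of age were required to interrupt study drug due to a partial clinical hold". For everyone else, section 1.2 says: "These subjects had palovarotene dosing interrupted on or around January 24, 2020". It adds that "The sponsor allowed dosing to resume as of March 26, 2020", subject to site-level approvals, with restarts expected to spread over several weeks.

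**The concern.** The pause was imposed by the regulator and the sponsor. Days on which a subject was not allowed to take drug say nothing about adherence, yet section 5.10 counts them as expected dosing days that were missed. The charge falls only on subjects who came back to treatment, because only for them does the pause lie between first and last dose.

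The interruption line has a related weakness. The pause far exceeds 14 days, so a restarter who was dosing daily when it began is counted as interrupted whatever else happened. The line then mixes a programme-wide event with individual decisions to stop and resume.

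At stake is whether the exposure and compliance tables in the final report can be read as describing how subjects took the drug.

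**Working it through.** The SAP gives no compliance figure to reproduce, so the check applies its formulas to its own dates.

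**Step 1: length of the pause.** From 24 January to 26 March 2020: 7 + 29 + 26 = 62 days, which is 62/14 = 4.4 times the interruption threshold. From the 4 December 2019 hold to the same date is 113 days. The second figure matters only for a subject under the hold who later restarted; section 3.1.4 provides for that case, while section 2.3 says treatment will not be restarted in children under 14. Both are minimum values, since individual restart dates are not given.

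**Step 2: compliance formula.** Take a restarter who missed no dose outside the pause. Let E be expected non-flare-up days (section 5.10) and P the pause days. The numerator is E − P and the denominator is E, so compliance = (E − P)/E. It is below 80% when P > 0.2E, that is, when E < 5P.

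**Step 3: non-flare-up dosing** (months converted at 30.5 days, as the SAP does).

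| P (days) | E (days) | (E − P)/E |
|---|---|---|
| 62 | 305 (10 months) | 243/305 = 79.7% |
| 62 | 365 | 303/365 = 83.0% |
| 62 | 731 | 669/731 = 91.5% |
| 62 | 1464 (48 months) | 1402/1464 = 95.8% |
| 113 | 549 (18 months) | 436/549 = 79.4% |
| 113 | 732 (24 months) | 619/732 = 84.6% |
| 180 (assumed) | 732 (24 months) | 552/732 = 75.4% |
| 180 (assumed) | 1098 (36 months) | 918/1098 = 83.6% |

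The 80% boundary is E = 5 × 62 = 310 days for the minimum pause and 5 × 113 = 565 days for the pause dated from the hold. At the 48-month maximum for non-flare-up treatment in Part C, the pause would have to exceed 0.2 × 1464 = about 293 days.

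**Step 4: flare-up dosing.** A cycle of 84 doses that straddles a 62-day pause has a first-to-last span of 84 + 62 = 146 days and scores 84/146 = 57.5%. Such a cycle falls below 80% once the pause exceeds 84/0.8 − 84 = 21 days.

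**Step 5: subjects who did not restart.** Their last dose precedes the pause, so P enters neither numerator nor denominator. With no other missed dose they score 100%.

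**Step 6: after the correction.** If pause days also leave the denominator, the restarter scores (E − P)/(E − P) = 100% whatever the pause length.

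**The case against.** Four arguments can be made for leaving the text alone.

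1. **Tolerability interruptions are reported elsewhere.** Section 7.1 tabulates and lists treatment-emergent adverse events leading to interruption. This stands. A reader might infer from section 5.9.2 that such interruptions are lost altogether; they are not. What remains merged with the pause is interruption for other subject-level reasons.
2. **The pause was a real interruption.** The SAP itself calls it one, so counting it is factually correct. That is fair as a description of exposure, but it does not justify a line that cannot be split, and it does not touch the compliance formula.
3. **The reporting window may exclude the pause.** Section 10 says the final report focuses on data after 28 February 2020, and section 1.1 says interim tables will not be rerun. If compliance were computed only up to the pause, or only from restart, the pause would lie outside first-to-last dose. But neither section 5.9.2 nor section 5.10 limits dose dates in this way, and section 3.9 says the document describes the final report. If that limit is intended, it has to be written down.
4. **Little depends on these tables.** Section 4.4 drops the formal per-protocol analyses, which is where an 80% rule would have mattered. This also stands, and it caps the importance of the point.

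**Conclusion.** The point holds. As written, section 5.10 with sections 3.2.3 and 3.2.4 lowers the compliance of every restarter whose compliance is computed across the pause, and leaves non-restarters untouched. Section 5.9.2 counts every subject on daily dosing who paused and restarted as interrupted.

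The size depends on dosing span. At the minimum 62-day pause the loss is 17.0 percentage points over a year, 8.5 over two years and 4.2 over 48 months. A reader might infer that the below-80% category mainly reflects the timing of approvals. The documents do not support that: at 62 days it requires fewer than 310 expected days of non-flare-up dosing, or a flare-up cycle straddling the pause. Longer pauses would widen the group, but their lengths are assumptions here.

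The calculation assumes no missed dose outside the pause and, in Step 3, no flare-up cycle overlapping it. The consequence is limited to descriptive exposure and compliance tables; no planned efficacy comparison rests on them. The change should still be made, because sections 5.8, 6.1, 6.2 and 7.9 already separate results around the pause and sections 5.7, 5.9.2 and 5.10 do not.

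**What to change.** - **Section 5.10:** define for each restarter an imposed-pause window, from the December 2019 hold or the January 2020 interruption to the actual restart date. Subtract those days from expected duration, for both non-flare-up dosing and flare-up cycles. Alternatively, compute compliance separately before the pause and after restart, in line with the split used in sections 5.8, 6.1 and 6.2.
- **Sections 5.7 and 5.9.2:** report the imposed pause on its own line, and count all other interruptions of at least 14 days separately, preferably by reason.
- **Reporting window:** state which dose dates the final-report exposure and compliance tables cover.

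The cost is SAP wording and one derived window per subject from dosing dates already held. No new data are needed and no dosing rule changes.
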